13. STATISTICAL CONSIDERATIONS

13.1 Study Design/Description

This is a single-arm, open-label, non-randomized, phase IIA trial to determine the immunogenicity of a prime and deferred-booster dosing schedule of a nonavalent prophylactic HPV vaccine (GARDASIL 9) among 9-11 year-old girls and boys. The primary endpoint analysis will be evaluating persistence and stability of serologic geometric mean titers (GMT) of HPV16/18 between 6, 12, 18, and 24 months after the prime dose/prior to administration of the second dose. If the HPV 16/18 antibody level at 12/18/24 months is not inferior to the HPV 16/18/24 antibody level at 6/12/18 months at a non-inferiority margin of 0.35 standard deviation, then the serologic GMT is considered as persistent and stable.

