13.4 Primary Objective, Endpoint(s), Analysis Plan

The primary objective of this study is to determine the persistence and stability of serologic geometric mean titer (GMT) of HPV 16/18 between 6, 12, 18, and 24 months after the prime dose and prior to the

administration of the second dose. The primary endpoints are the HPV 16/18 antibody levels at 6, 12, 18, and 24 months. To address the primary objective, the primary endpoint analysis will be evaluating persistence and stability of serologic geometric mean titers (GMT) of HPV16/18 between 6, 12, 18, and 24 months after the prime dose/prior to administration of the second dose. We first propose to perform a one-sided paired t test to compare the difference in the mean of the log-transformed antibody levels between 6 and 12 months, between 12 and 18 months, and between 18 and 24 months respectively, to evaluate whether the GMT at 12/18/24 months, respectively, is not inferior to the GMT at 6/12/18 months. Comparing the difference in the mean of the log-transformed antibody levels is equivalent to comparing the logarithm of the ratio of GMTs since GMT is equal to the exponentiation of log-transformed mean. Bonferroni correction will be used to correct for multiple comparisons (6 vs. 12, 12 vs. 18 and 18 vs. 24).

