The protocol was originally designed to assess the serologic response in girls. Amendment 4 includes the addition of a cohort of boys. Due to limits in the study completion timeline and available study budget, a smaller number of boys than girls will be included in the study to generate pilot data on the serologic response in boys. Boys have been shown to mount a higher serologic response than girls. Therefore, we expect boys and girls to have different responses to the vaccine and will perform the primary analyses for girls and boys separately. For girls, with a sample size of 100 and an overall significance level of 5% (based on Bonferroni correction, i.e. a 1.67% significance level for each test), there will be at least 90% power to detect a non-inferiority margin no greater than 0.35 standard deviations [23]. For boys, with a sample size of 39 and an overall significance level of 5%, there will be at least 80% power to detect a non-inferiority margin no greater than 0.50 standard deviations. In addition, similar to the analysis performed by Safaeian et al. [13], we will also evaluate the stability by categorizing the changes in antibody level from 6 months to 12 months. Specifically, a participant's antibody level at 12 months either remains within two-fold of the level at 6 months (considered as stable) or decreases/increases more than two-fold of the level at 6 months (same for the changes from 12 months to 18 months and from 18 months to 24 months). Percentage of participants whose type-specific antibody levels decrease, increase, or remain stable between the 6 and 12 month study visits, between the 12 and 18 month study visits and between the 18 month and 24 month study visits will be reported along with the associated 95% confidence interval. For girls, a sample size of 100 will produce a two-sided 95% confidence interval with a width ≤ 0.203 based on the exact method approach. For boys, a sample size of 39 will produce a two-sided 95% confidence interval with a width ≤ 0.328 based on the exact method approach.

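### Section 13.1 concludes stability from a one-sided non-inferiority test that sets no limit on a rise; the test supports persistence only

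*Combined protocol and SAP*

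**What the plan says.** Sections 1.1 and 8.1 set a primary objective and endpoint with two parts, persistence and stability, for the HPV 16/18 GMT from month 6 to month 24.

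- **Decision rule (13.1).** When the level at 12, 18 or 24 months is not inferior to the one before it "at a non-inferiority margin of 0.35 standard deviation, then the serologic GMT is considered as persistent and stable". No other rule in the plan yields a verdict.
- **Test (13.4).** "We first propose to perform a one-sided paired t test to compare the difference in the mean of the log-transformed antibody levels", the purpose being "to evaluate whether the GMT at 12/18/24 months, respectively, is not inferior to the GMT at 6/12/18 months". Three adjacent intervals are tested: "Bonferroni correction will be used to correct for multiple comparisons (6 vs. 12, 12 vs. 18 and 18 vs. 24". The level is "an overall significance level of 5% (based on Bonferroni correction, i.e. a 1.67% significance level for each test".
- **Second look at stability (13.4).** Each participant's level at the later visit "remains within two-fold of the level at 6 months (considered as stable) or decreases/increases more than two-fold of the level at 6 months", and likewise for the other two intervals. The percentages that fall, rise or stay stable are reported with 95% confidence intervals. No pass threshold is set, and nothing says how these percentages bear on the section 13.1 conclusion.

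Neither section gives an upper limit for the GMT ratio or an equivalence test.

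**The concern.** A test against a lower margin has one possible positive finding: the GMT has not dropped by more than the margin. That is persistence. Section 13.1 adds stability to the same result, although the test is blind to upward movement. The participant-level definition in section 13.4 works in both directions, so the plan holds two meanings of stable and does not say which one governs.

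At stake is the label on half of the primary objective. No study vaccine is given between the prime dose and the month 24 booster. A marked rise in GMT over that period would call for an explanation, such as a shift in the assay or an exposure that was not captured. Under section 13.1 the same rise makes a declaration of stability more certain.

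**Working it through.** **Inputs.** From section 13.4: 100 girls, margin 0.35 SD; 39 boys, margin 0.50 SD; one-sided level 0.05/3 = 1.67% per test. Section 13.1 gives only 0.35 SD. The documents do not define the SD, so I take it as the SD of the paired log differences. All probabilities are per interval.

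**1. The plan's own power.** The pass probability is the chance that a noncentral t with n − 1 degrees of freedom and noncentrality (margin + δ)·√n exceeds the critical value, where δ is the true change in SD units.

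- Girls, δ = 0: noncentrality 0.35 × √100 = 3.50, critical value 2.158, power 90.9%. The plan says at least 90%.
- Boys, δ = 0: noncentrality 0.50 × √39 = 3.12, critical value 2.208, power 81.6%. The plan says at least 80%.
- With 1.67% split over two tails, the figures would be 85.4% and 72.9%, which miss the stated power. The plan's numbers are those of a one-sided test without an upper bound.

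**2. What a rise does.**

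| True change (SD) | Girls, 0.35 SD | Boys, 0.50 SD |
|---|---|---|
| −0.35 | 1.67% | 11.1% |
| 0 | 90.9% | 81.6% |
| +0.10 | 99.0% | 93.4% |
| +0.20 | 99.95% | 98.3% |
| +0.35 | about 100% | 99.9% |
| +0.50 | about 100% | about 100% |

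For girls, an observed change of exactly zero gives a statistic of 3.50 against 2.158 when the sample SD equals the SD used for the margin. Every observed rise then passes. Zero change would fail only if the sample SD exceeded that value by a factor of 3.50/2.158 = 1.62.

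**3. Against the two-fold categories.** The documents give no SD on the log scale, so I assume 0.3 to 1.0 for the SD of the natural-log differences. The share of participants whose level more than doubles is 1 − Φ((ln 2 − ln GMR)/SD), where GMR is the GMT ratio.

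- GMR 2.5: 77% of girls increased at SD 0.3 and 59% at SD 1.0; 23% to 36% stable over the range. The section 13.1 rule passes with probability about 100%.
- GMR 1.25: the rule also passes almost surely, and 50% to 94% of girls are stable under section 13.4.

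The share that is stable depends on the SD even without any shift. At SD 1.0 and GMR 1 it is 2Φ(0.693) − 1 = 51%. The categories therefore need the GMT ratio and its interval beside them.

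**4. A two-sided rule, for comparison.** With 1.67% per side and the same margins, power at no change is 2 × 0.9085 − 1 = 82% for girls and 2 × 0.8161 − 1 = 63% for boys.

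**5. Sensitivity to the SD definition.** If the SD is that of the log titres and visits are correlated at zero or above, the girls' statistic at no observed change is at least 3.50/√2 = 2.47, still above 2.158. For boys at the section 13.1 margin it is 0.35 × √39 = 2.19 under the paired-difference reading, just below 2.208, and 1.55 at zero correlation. A small rise could then fail.

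**The case against.** The best defence is that section 13.4 is the operative section and largely keeps the two ideas apart. The t test addresses non-inferiority, and stability is then evaluated through categories that run in both directions. Decline is the real risk after a single dose, so a one-sided test is apt. Nothing in the documents suggests that a 2.5-fold rise is likely, and HPV vaccination outside the study is met by monthly reminders and removal from study (sections 5.5, 7.3 and 8.4).

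Most of this stands. The one-sided test is right for persistence, and the stated power is correct for it. But section 13.1 is where the conclusion is defined, and section 13.4 itself introduces the t test as the first step in evaluating both parts of the objective. The categories have no threshold and no route to the verdict.

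Several stronger readings are tempting and do not hold:

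- *Section 13.4 treats any rise as not stable.* It does so only for a participant whose level more than doubles.
- *A drifting GMT would pass.* For girls, a true fall of 0.35 SD in one interval passes 1.67% of the time. Slow decline spread over several intervals is a consequence of testing adjacent visits only, which is a separate matter from sidedness.
- *Stability is not examined, or a rise would be hidden.* Section 13.4 reports the percentage increased with a confidence interval.
- *The pass rates at +0.10 and +0.20 SD are errors.* Those changes lie within 0.35 SD of zero, and a pass there is no false verdict.

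**Conclusion.** Wrong as written, minor in severity. The section 13.1 rule draws a conclusion about stability that its test cannot support. For girls, a true rise of 0.35 SD or more in an interval passes with probability about 100%, and a rise large enough to place most participants in the increased category of section 13.4 would still be declared stable.

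The girls' result rests on reading the SD as that of the paired log differences, and it survives the other reading when visits are not negatively correlated. The 2.5-fold illustration rests on an assumed log-scale SD of 0.3 to 1.0.

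A reader might infer that the trial needs a formal equivalence test. The documents do not require one: the fault lies in the wording of a conclusion, and the plan already has a two-directional summary on which to base statements about stability.

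**What to change.** In section 13.1, let the one-sided test conclude only that the GMT is persistent, meaning not inferior to the preceding visit, and remove stability from that conclusion. State that any claim of stability rests on the two-fold categories of section 13.4 with their 95% confidence intervals, reported with the two-sided confidence interval for the GMT ratio. A 96.7% interval (1.67% per side) has a lower limit that matches the test. Align the sentences in sections 13.4 and 13.5 that present the one-sided test as evaluating both properties.

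The cost is a few sentences and one more confidence limit from the same analysis. Sample sizes and stated power do not change.

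A two-sided equivalence rule is optional. Its power at no change, about 82% for girls (0.35 SD) and 63% for boys (0.50 SD), would have to be stated. Restoring 90% and 80% would take about 118 girls and 49 boys completing, or 118/0.7 ≈ 169 and 49/0.7 = 70 enrolled, against 143 and 57 planned; section 13.4 cites timeline and budget limits. The margin would also not line up with two-fold: at the assumed SDs, 0.35 SD is a change of exp(0.35 × 0.3) = 1.11-fold to exp(0.35 × 1.0) = 1.42-fold.

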13.2 Randomization/Stratification

This is a single-arm, open-label and non-randomized trial so no randomization, stratification or blocking will be performed. Also, no formal interim analysis is planned.

13.3 Accrual and Feasibility

We plan to accrue 143 eligible girls and 57 eligible boys to receive the deferred-booster schedule of the Gardasil 9. With an anticipated attrition rate of 30%, we expect to have at least 100 girls and 39 boys to complete the 30-month visit. We anticipate to enroll 6-8 participants/per month for each study site and estimate that it will take approximately 12-17 months to complete accrual.

13.4 Primary Objective, Endpoint(s), Analysis Plan

The primary objective of this study is to determine the persistence and stability of serologic geometric mean titer (GMT) of HPV 16/18 between 6, 12, 18, and 24 months after the prime dose and prior to the

administration of the second dose. The primary endpoints are the HPV 16/18 antibody levels at 6, 12, 18, and 24 months. To address the primary objective, the primary endpoint analysis will be evaluating persistence and stability of serologic geometric mean titers (GMT) of HPV16/18 between 6, 12, 18, and 24 months after the prime dose/prior to administration of the second dose. We first propose to perform a one-sided paired t test to compare the difference in the mean of the log-transformed antibody levels between 6 and 12 months, between 12 and 18 months, and between 18 and 24 months respectively, to evaluate whether the GMT at 12/18/24 months, respectively, is not inferior to the GMT at 6/12/18 months. Comparing the difference in the mean of the log-transformed antibody levels is equivalent to comparing the logarithm of the ratio of GMTs since GMT is equal to the exponentiation of log-transformed mean. Bonferroni correction will be used to correct for multiple comparisons (6 vs. 12, 12 vs. 18 and 18 vs. 24).

The protocol was originally designed to assess the serologic response in girls. Amendment 4 includes the addition of a cohort of boys. Due to limits in the study completion timeline and available study budget, a smaller number of boys than girls will be included in the study to generate pilot data on the serologic response in boys. Boys have been shown to mount a higher serologic response than girls. Therefore, we expect boys and girls to have different responses to the vaccine and will perform the primary analyses for girls and boys separately. For girls, with a sample size of 100 and an overall significance level of 5% (based on Bonferroni correction, i.e. a 1.67% significance level for each test), there will be at least 90% power to detect a non-inferiority margin no greater than 0.35 standard deviations [23]. For boys, with a sample size of 39 and an overall significance level of 5%, there will be at least 80% power to detect a non-inferiority margin no greater than 0.50 standard deviations. In addition, similar to the analysis performed by Safaeian et al. [13], we will also evaluate the stability by categorizing the changes in antibody level from 6 months to 12 months. Specifically, a participant's antibody level at 12 months either remains within two-fold of the level at 6 months (considered as stable) or decreases/increases more than two-fold of the level at 6 months (same for the changes from 12 months to 18 months and from 18 months to 24 months). Percentage of participants whose type-specific antibody levels decrease, increase, or remain stable between the 6 and 12 month study visits, between the 12 and 18 month study visits and between the 18 month and 24 month study visits will be reported along with the associated 95% confidence interval. For girls, a sample size of 100 will produce a two-sided 95% confidence interval with a width ≤ 0.203 based on the exact method approach. For boys, a sample size of 39 will produce a two-sided 95% confidence interval with a width ≤ 0.328 based on the exact method approach.

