(<https://www.cdc.gov/mmwr/volumes/65/wr/mm6549a5.htm>; <https://www.cdc.gov/hpv/hcp/2-dose/clinician-faq.html>). Participants from the youngest of the licensed age groups (9-11 years) are selected for this proof-of-principle study given the potential for younger age children to mount higher immune titers [15], and the fact that immune responses to a single dose or two doses of the HPV vaccines among girls aged 9-14 years appear to be comparable to antibody responses of 3 doses in young women 15-25 years old [9]. The study hypothesis is that a single dose of the nonavalent HPV vaccine will induce persistent and stable serological responses for up to 24 months to all 9 vaccine HPV types in girls and boys 9-11 years of age.

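### The hypothesis is persistence to 24 months, but every planned comparison is between adjacent visits and no month-24/month-6 estimate is pre-specified.

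*Combined protocol and SAP*

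**What the plan says.** All references are to the combined protocol and SAP.

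- **Hypothesis (Section 2.3):** "a single dose of the nonavalent HPV vaccine will induce persistent and stable serological responses for up to 24 months".
- **Decision rule (Section 13.1):** "If the HPV 16/18 antibody level at 12/18/24 months is not inferior to the HPV 16/18/24 antibody level at 6/12/18 months", with a margin of 0.35 SD, the response counts as persistent and stable. The second type list looks like a slip for 16/18.
- **Primary tests (Section 13.4):** one-sided paired t tests on log antibody level, "between 6 and 12 months, between 12 and 18 months, and between 18 and 24 months respectively, to evaluate whether the GMT" at the later visit is non-inferior. The multiplicity adjustment covers these three comparisons only: "Bonferroni correction will be used to correct for multiple comparisons (6 vs. 12, 12 vs. 18 and 18 vs. 24".
- **Power (Section 13.4):** for 100 girls, "there will be at least 90% power to detect a non-inferiority margin no greater than 0.35 standard deviations"; for 39 boys, "there will be at least 80% power to detect a non-inferiority margin no greater than 0.50 standard deviations". Each test is at 1.67%.
- **Individual stability (Section 13.4):** a child's month-12 level "either remains within two-fold of the level at 6 months (considered as stable" or changes by more than that, with the "same for the changes from 12 months to 18 months and from 18 months to 24 months".
- **Secondary analyses (Section 13.5):** the same adjacent tests and categories for the other seven types. A mixed model uses months 6, 12, 18 and 24 together, but its stated purpose is the effect of BMI on change.

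No section names a month-24 versus month-6 difference, ratio, interval, margin or category.

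**The concern.** Each step takes the previous visit as its new reference. A response that drifts down a little every six months can pass each comparison while the drift accumulates, and no planned output shows the accumulated change with its uncertainty. The trial could report persistence to 24 months without a direct estimate of how month 24 compares with month 6.

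If the same imputed data enter all three tests, a reader can add the three mean log differences to get the 24/6 point estimate. The paired confidence interval cannot be recovered that way, because it depends on the covariances between steps.

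The two-fold table has the same feature. A child whose level falls 1.9-fold in each interval is counted stable three times, although the overall fall is 1.9³ = 6.9-fold.

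**Working it through.** **Inputs.** n = 100 girls and 39 boys; one-sided alpha 0.05/3 per test; margins 0.35 SD (Sections 13.1 and 13.4) and 0.50 SD (boys, Section 13.4 power statement only). The documents do not say which SD is meant; I take it as the SD of the paired log difference over one step. Calculations are per HPV type with complete data.

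**1. The plan's own power.** Noncentral t, no true change, noncentrality = margin × √n.
- Girls: 0.35 × √100 = 3.50, critical t (99 df) = 2.158, power 0.909. Stated: at least 0.90.
- Boys: 0.50 × √39 = 3.12, critical t (38 df) = 2.208, power 0.816. Stated: at least 0.80.

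Both reproduce, which supports this reading of the SD.

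**2. Largest equal observed loss that passes every step.** A step passes if the observed loss is below margin − t/√n.
- Girls: 0.35 − 2.158/10 = 0.134 SD; three steps total 0.40 SD, above the 0.35 SD single-step margin.
- Boys, margin 0.50: 0.50 − 2.208/√39 = 0.50 − 0.354 = 0.146 SD; total 0.44 SD.
- Boys, margin 0.35: 0.35 − 0.354 = −0.004 SD. Boys then cannot pass with equal step losses of any size.

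**3. How often the rule passes.** Simulation with 20,000 runs per setting, normal data, equal losses per step, and four assumed correlation structures between visits: compound symmetry, AR(1) with 0.8 and 0.9, and random walk. Share of trials in which all three steps pass:

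| True total loss | Girls, 0.35 SD | Boys, if 0.50 SD |
|---|---|---|
| 0 | about 73-75% | about 50-54% |
| 0.35 SD | about 9-19% | about 10-20% |
| 0.60 SD | 0.1-1.7% | about 1-5.5% |

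**4. Guaranteed cumulative limit.** Three passes imply 3 × 0.35 = 1.05 SD for girls and, if the margin is 0.50, 3 × 0.50 = 1.50 SD for boys. These are worst-case sums; row 3 of the table shows that far smaller true losses already rarely pass.

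**5. What a direct contrast would give.** The SD of month 24 minus month 6, in one-step SD units, is 1.00 (compound symmetry), 1.56 (AR 0.8), 1.65 (AR 0.9) or 1.73 (random walk). The 95% half-width is t(0.975) × that SD/√n.
- n = 100: 1.984 × 1.00/10 = 0.20 up to 1.984 × 1.73/10 = 0.34 SD.
- n = 39: 2.024 × 1.00/6.245 = 0.32 up to 2.024 × 1.73/6.245 = 0.56 SD.

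**6. Fold scale, conditional.** The SD in ln units is not given. For an assumed 0.5 to 0.9, an observed total of 0.40 SD in girls is a GMT fall of 1 − exp(−0.4026 × 0.5) = 18% to 1 − exp(−0.4026 × 0.9) = 30%. For boys at 0.44 SD (margin 0.50) it is 20% to 33%.

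**The case against.** The plan is coherent on its own terms. The objective speaks of stability between the four visits, Section 13.1 defines persistence by adjacent comparisons, and the tests, alpha and power follow. Section 2.3 gives a 24-month horizon but does not name month 6 as a fixed reference. Levels at all four visits are primary endpoints, the 24/6 point estimate can be derived, and the mixed model could yield the contrast. The boys' cohort is described as pilot data. All of this stands. What it leaves open is one interval: the step results do not supply it, and a mixed-model contrast chosen after the data are seen is not pre-specified.

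A reader might infer more than the documents support:

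- **That the rule accepts losses near 1.05 SD.** It does not in practice. All three tests must pass, and for girls a true total of 0.60 SD passes in 2% of trials or fewer.
- **That the stepwise rule is more lenient than a direct test.** This depends on a correlation the documents do not give. At a true loss of 0.10 SD per step in girls, all steps pass in 15.5% of trials against 4.0% for a direct test (margin 0.35 SD of the 18-month difference, alpha 1.25%) under exchangeable errors, but in 24.4% against 29.9% with independent steps.
- **That a whole cohort could fall 1.9-fold per interval unnoticed.** ln 1.9 = 0.64, which at an assumed SD of 0.9 is 0.71 SD per step, far above the 0.134 SD that can pass.
- **That the boys' figures are settled.** The 0.50 SD appears only in a power statement; the decision rule gives 0.35 SD without distinction by sex.

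**Conclusion.** The concern holds in a limited form. The hypothesis reaches to 24 months, every planned persistence analysis compares adjacent visits, and the direct month-24/month-6 estimate is not pre-specified. That structural point needs no assumption.

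Its practical reach is moderate steady waning. For girls the rule can be met with an observed total loss of up to 0.40 SD in equal steps, and it passes a true total loss of 0.35 SD in about 9-19% of trials. For boys the corresponding observed total is 0.44 SD only if 0.50 SD is the decision margin; under 0.35 SD none of the boys' loss figures apply.

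These sizes rest on reading the SD as that of the paired log difference and on assumed correlations between visits. The percentage falls rest further on an assumed SD in ln units. The primary tests are not invalid and their power is correctly stated. The change is worth making because it is nearly free and bears on the trial's main conclusion.

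**What to change.** - Keep the three adjacent primary tests, their alpha and their power.
- In Section 13.4, pre-specify for HPV16 and HPV18, separately for girls and boys, the paired month-24/month-6 GMT ratio with its 95% CI. Make it a supportive estimate from the same imputed data sets, with no hypothesis test.
- Add a month-6-to-24 row to the two-fold table.
- Report the ratio and CI beside any statement of persistence to 24 months, so that three adjacent passes are not described as non-inferiority of month 24 to month 6.

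Cost: one extra contrast per type and sex, on blood already scheduled at months 6 and 24 (Sections 7.1 and 10.2), with no alpha spent. The CI may be wider than for a single step: half-width 0.20-0.34 SD at n = 100 and 0.32-0.56 SD at n = 39.

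### The Bonferroni split counts three intervals but not the two HPV types, and the plan does not say whether any or all of the six primary tests per sex must pass

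*Combined protocol and SAP*

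**What the plan says.** Section 13.4 defines the primary endpoints: "The primary endpoints are the HPV 16/18 antibody levels at 6, 12, 18, and 24 months". The method is a "one-sided paired t test to compare the difference in the mean of the log-transformed antibody levels", applied to 6 vs. 12, 12 vs. 18 and 18 vs. 24 months, to show that the later GMT is not inferior to the earlier one. On multiplicity it says: "Bonferroni correction will be used to correct for multiple comparisons (6 vs. 12, 12 vs. 18 and 18 vs. 24".

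The power statement for girls uses "an overall significance level of 5% (based on Bonferroni correction, i.e. a 1.67% significance level for each test", 100 girls, and claims "at least 90% power to detect a non-inferiority margin no greater than 0.35 standard deviations". For boys it claims at least 80% power at a margin of 0.50 SD with 39 boys, also at an overall 5%. Girls and boys are analysed separately.

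Section 9.1 has HPV16 and HPV18 serology measured by ELISA. Section 13.4 also reports results by type: "Percentage of participants whose type-specific antibody levels decrease, increase, or remain stable". No section defines a combined 16/18 titre or divides alpha between the types. The waiver of multiplicity adjustment in 13.5 covers secondary and exploratory analyses only.

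The only written success rule is in 13.1. It is one condition, naming HPV 16/18 and all the later visits together, and it leads to one conclusion: that the GMT is persistent and stable.

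**The concern.** Two types over three intervals make six primary tests in each sex, while the correction divides by three. The overall 5% is therefore not tied to any defined set of claims. A reader cannot tell whether it covers HPV16 and HPV18 together or each one alone, or whether one pass is enough or all are needed.

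The choice changes both figures attached to the primary conclusion. Under an any-pass rule over both types, the error exceeds 5%. Under an all-pass rule, the error is well below 5%, but the quoted power describes one test of one type, not the conclusion being drawn.

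**Working it through.** **Inputs (13.4).** One-sided paired t test; girls n = 100, margin 0.35 SD; boys n = 39, margin 0.50 SD; 1.67% per test.

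**Assumptions.** For power, the true change is zero, because the plan states no expected decline. The SD is taken as that of the paired log difference; the plan does not say which SD it means, but this choice reproduces its figures. The HPV16/18 correlation is not given, so it is varied from 0 to 0.9. The correlation between adjacent interval changes is set to 0 or -0.5.

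**1. Reproduce the stated power.** Power = 1 - F(t(1-α, n-1)), where F is the noncentral t distribution with n-1 degrees of freedom and noncentrality margin × √n.
- Girls: noncentrality 0.35 × √100 = 3.50; power 90.9% at 1.67%.
- Boys: noncentrality 0.50 × √39 = 3.12; power 81.6% at 1.67%.

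Both statements reproduce, as the power of a single test.

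**2. Error if any pass counts (all six changes at the margin).**
- One type, three tests: bound 3 × 1.67% = 5%.
- Both types, six tests: bound 6 × 1.67% = 10%. If independent: 1 - (1 - 0.01667)^6 = 9.6%.
- Simulated with correlated types:

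| HPV16/18 correlation | Error over six tests |
|---|---|
| 0 | 9.6-9.7% |
| 0.5 | 8.9-9.1% |
| 0.8 | 7.8-7.9% |
| 0.9 | 7.0-7.1% |
| 1 | about 5% |

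**3. Error and power if all six must pass.** The conclusion is false if any one change is at or beyond its margin, and that one test passes with probability at most its own level. The error is therefore at most 1.67%, or at most 5% if each test is run at 5%. With six independent tests, joint power is the single-test power to the sixth power:
- At 1.67%: girls 0.9085^6 = 56%; boys 0.8161^6 = 30%.
- At 5% (single-test power 96.65% and 92.24%): girls 0.9665^6 = 82%; boys 0.9224^6 = 62%.

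Simulated over type correlations 0 to 0.9 and both interval correlations:

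| Level per test | Girls, all six | Boys, all six |
|---|---|---|
| 1.67% | about 54-68% | about 25-46% |
| 5% | about 81-87% | about 60-72% |

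**4. Holding 5% over six separate claims.**
- Plain Bonferroni, 5%/6 = 0.83% per test: power 85.4% (girls) and 72.9% (boys), below the stated 90% and 80%.
- Holm over the six tests: error about 4-5%; average per-test power about 94-96% (girls) and 86-88% (boys) with no true change (type correlation 0 to 0.8).

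Holm never rejects less often than Bonferroni over the same six tests. If some changes are real declines, the per-test power for the others falls, but not below the plain Bonferroni figures.

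**The case against.** The best defence is that conclusions are meant separately for each type. Section 13.4 lists the Bonferroni family as the three intervals, and 13.5 applies the parallel test to each HPV type. On that reading each type is held at 5% and the single-test power stands as quoted. This is possible, but the plan does not say it, and 13.1 puts both types into one condition with one conclusion.

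Two stronger readings are tempting. A reader might infer that the trial's error rate is really near 10%. That needs a rule under which any one pass supports the claim, which the plan does not state, and near-zero correlation between HPV16 and HPV18. The wording of 13.1 reads more naturally as a rule that everything must pass, which keeps the error at or below 1.67%.

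A reader might also infer that 5% over six tests cannot be had at the stated power. That is true of plain Bonferroni over six. It is not true of Holm, whose average per-test power exceeds 90% and 80% when nothing truly changes.

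It is also fair to say that this is a single-arm Phase IIA trial and that the boys are included to give pilot data. Strict error control across types matters less there.

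**Conclusion.** Wrong as written. The stated overall 5% comes from a split that leaves out the second primary HPV type, and the rule that would give the 5% a meaning is missing. The size depends on that rule:
- **Claims by type:** 5% for each type is correct, and up to 10% over both.
- **Any pass on either type:** about 7-10% with all changes at the margin, for type correlation 0.9 to 0.
- **All six must pass:** error at most 1.67%, so the split is unnecessary. The quoted 90% and 80% are not the power of the conclusion, which is about 54-68% (girls) and 25-46% (boys).

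Only the per-type reading keeps both stated figures, and it is not written down. The documents do not establish an actual 10% error or a power shortfall that cannot be avoided. All powers here assume no true change and a margin scaled to the SD of the paired log difference. The point carries less weight for the boys.

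**What to change.** In 13.4, define the primary family in each sex as two HPV types by three intervals, state the decision rule, and align 13.1 with it. Then take one of these:

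1. **Separate claims by type and interval (any pass may be claimed).** Replace Bonferroni with Holm over the six tests at an overall one-sided 5%, and restate the power on that basis, with its assumption of no true change. The downside is a stricter first step: 0.83% instead of 1.67%.
2. **All six must pass.** Test each at one-sided 5% with no split, and quote the joint power (about 81-87% girls, 60-72% boys) with the assumed correlations.
3. **Keep 1.67%.** State that the 5% is per HPV type and that the level over both types is up to 10%.

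Each option costs a few sentences and restated error and power figures. None needs more participants or new data. The choice should be fixed before the serology results are analysed.
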